5.3 Withdrawal

Possible reasons for withdrawal:

1. Withdrawal of consent.

2. Loss of capacity/ability to carry out study requirements as deemed by participant's primary medical team. Loss of capacity will be monitored by the patients Phase 1-2 trial team.

- 3. Safety reasons
- 4. Participant's decision to withdraw.

5. Severe non-compliance to protocol as judged by the investigator and/or Sponsor.

If at any time a participant expresses a wish to withdraw consent for ongoing study participation, the following procedures will be observed:

1. Withdrawal of consent will be clearly documented in the study documentation and the study participant's medical record.

2. No further clinical data will be collected from the study participant. However, existing clinical data held will be retained and may still be used in future research by researchers who have a legitimate interest in the study data.

3. The study participant's privacy will be respected and preserved.

If a participant consents to the study but subsequently becomes unable to give consent, they will be withdrawn from the study; the reason for withdrawal will be documented by the team but no further information will be collected. Previously obtained data will still be used in the study.

5.4 Recruitment

Patients in screening for a phase 1-2 trial will be informed of this feasibility study and given the PIS by their treatment team. Patients must not have commenced treatment in order to qualify to join the feasibility study. For trial entry a patient must fulfil all inclusion criteria and no exclusion criteria; this preliminary check against eligibility will be conducted by the patient's treating clinician.

A patient can be supported in this study by a carer e.g. if the patient does not have access to a suitable device but a carer is willing to provide access to one for them. However the role of the carer should be limited to support in accessing the tool and they should not complete the videos or questionnaires on the patients behalf.

5.5 Consent

All patients are required to sign an informed consent prior to taking part in this feasibility study. All potential participants will receive a PIS at first point of identification of the patient by the clinician and provided with sufficient time to consider this and ask questions. The PIS will outline the benefits and risks of taking part in this study. Once potential participants have had sufficient time to consider the information in the PIS they will be invited to consent for the study. Once consent is obtained the patient will be formally screened against eligibility criteria.

It should be made clear to the potential study participant that consent is voluntary and can be withdrawn without giving reasons and without prejudicing their ongoing/future care. If a potential participant fails screening or withdraws from the study, where possible, the reason for this will be documented.

Consent will be taken by a researcher who is appropriately trained and who has been delegated by the PI (Principal Investigator) to undertake this activity (and this is clearly documented on the delegation log). No study-related activities can be undertaken prior to consent.

The original, signed copy of the PIS and consent form(s) will be retained in the Investigator Site File, with a copy in the participant notes and a copy provided to the participant.

5.6 Prior to C1D1

The following information will be collected from patients at baseline in their screening period before being included in a specific phase 1-2 trial

- Patient demographics (age in years, year of birth, ethnicity, sex and tumour type)
- Quality of life questionnaire
- WHO performance status (World Health Organisation)
- Treatment start date
- Type of drug: targeted therapy/immunotherapy/other

5.7 Trial arms

After the screening period is complete, participants will be allocated to one of the three arms based on an allocation schedule assigned by site as follows:

- NKI 1;2;3
- VHIO- Spain 2;3;1
- INT Italy: 3;1;2
- Cambridge UK: 1;2;3
- Heidelberg Germany 3;1;2

Where (1) is PROACT 2.0 video; (2) is PROACT 2.0 digital questionnaire; and (3) is standard QoL monitoring. The arm they are allocated to will be recorded. All arms will last for 4 weeks.

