4.2 Trial Population

All potential study participants will be seen and assessed against eligibility criteria whilst already enrolled (cannot have started treatment) or attending for consideration for participation in a phase 1 or 2 clinical trials. Study participants will be selected by treating physicians from the several Cancer Core Europe centres participating in the DART WP12 project. Potential participants will be provided with a patient information sheet (PIS) and invited to voluntarily consent to participate in the feasibility study. It should be made clear to the potential trial participant that consent is voluntary and can be withdrawn at any time without any impact on their ongoing medical care.

If a potential participant declines entry into the study, the reasoning for this will be documented in the screening log where possible.

Potential study participants should be given sufficient time to consider participation in this study before consent is elicited. No activities for the study can be undertaken before consent had been obtained. After consent has been received the patient will be formally assessed for eligibility for the study against inclusion and exclusion criteria of the study protocol.

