5.2 Exclusion criteria

A potential participant who meets any of the following criteria will be excluded from participation in this study:

- 1. Not capable of using mobile phone applications, or no carer who is willing to and able to use the applications on the participants behalf.
- 2. Enrolled in a phase 1-2 anticancer drug trial that includes a QoL questionnaire, where inclusion of an additional QoL would interfere with the study's intended QoL measurements. This is at the investigator's discretion.

A patient can be supported in this study by a carer e.g. if the patient does not have access to a suitable device but a carer is willing to provide access to one for them. However, the role of the carer should be limited to support in accessing the tool and they should not complete the videos or questionnaires on the patients behalf.

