8 DATA MANAGEMENT

Data collected from this study will be done so in line with CCE-DART SOPs (standard operating procedures) and processed in accordance with EU regulation 2016/679 (GDPR). For sites in the UK data will be processed in accordance with The Data Protection Act 2018, General Data Protection Regulations 2018 and Freedom of Information Act 2000. Storage will be secure; physically within a secure area with limited access and electronically on secure servers or in secure cloud environments, behind appropriate firewalls, with regular back up. Each centre participating in the project will be responsible for protecting the confidentiality of the participants data that are collected.

The protection of personal data will comply with the local, national and European or UK standards (as applicable) for protection of privacy and confidentiality. In all cases, this will include the pseudonymisation of each participant, by replacing their name by a code that will make any direct identification impossible. This code (trial identifier based on study, site and chronological order e.g. PRONL001; PRONL002) will be used in all exchanges of information related to this participant. Sensitive hard copy records such as medical and trial-related records will be kept in a key-locked, access-restricted place, and computer access to sensitive electronic data will be password protected.

Access to this information and to the identity of the study participants will be strictly restricted to the physicians in charge of the participant and with their explicit authorisation, to data managers in charge of the study, study monitors and authorised regulatory bodies.

The pseudonymised data (primary data and the data resulting from CCE-DART analyses) will be accessible only to project partners and to the scientific community under the controlled access mode. The applicant credentials, research purposes and commitment of preserving data confidentiality will be carefully checked by the project Steering Committee before allowing access to data. The project will design and implement a storage system for processed data (defined in the master Data Management Plan).

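### Section 5.7 prints a fixed arm order for each site with no chance element or concealment, so the selecting physician can foresee the next arm and tool-arm adherence is open to selection

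*Protocol*

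**What the plan says.** Protocol section 5.7 places allocation after screening and sets the method: "participants will be allocated to one of the three arms based on an allocation schedule assigned by site as follows". The printed orders are 1;2;3 for NKI and Cambridge, 3;1;2 for INT and Heidelberg, and "VHIO- Spain 2;3;1". The codes follow: "Where (1) is PROACT 2.0 video; (2) is PROACT 2.0 digital questionnaire; and (3) is standard QoL monitoring". Two of the three arms therefore use the app. The protocol does not call the allocation random, and it describes no concealment, no central release and no variation in the order.

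On who chooses the patients, section 4.2 states: "Study participants will be selected by treating physicians from the several Cancer Core Europe centres participating in the DART WP12 project". Section 5.4 adds that "this preliminary check against eligibility will be conducted by the patient's treating clinician". Patients must enter before starting treatment in their drug trial (sections 4.2 and 5.4).

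The primary outcomes in section 3.2.1 are screen failures and withdrawals, and compliance with daily use over 28 days, with 75% as the acceptable level. Section 7.1 plans 60 patients, up to 12 at each of five sites, and descriptive statistics only.

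**The concern.** Allocation after consent and screening protects against selection only if nobody can work out the assignment beforehand. Here the order is in the protocol, and a site can count its own entrants. A physician deciding whom to approach can tell whether the next place is video, app questionnaire or standard monitoring.

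An obvious and well-meant response is to approach less confident app users when the standard arm is next, and more confident ones when a tool arm is next. The tool arms would then hold fewer weaker users than the population the study is meant to inform. Adherence would look better and withdrawals fewer, and both are primary outcomes. The bias would run towards declaring the tools feasible.

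It would also be hard to see afterwards. Section 5.6 collects age and WHO performance status at baseline but no measure of digital ability. Section 4.2 asks for reasons when a patient declines, but no record is described for patients who were never approached.

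**Working it through.** **The plan's own figures.** 5 sites × 1 patient per month × 12 months = 60, and 5 × 12 = 60, as stated. Pre-screens: 60 × 1.10 = 66, as stated.

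**Balance is not the problem.** If each order repeats over 12 patients, each site puts 4 in each arm, giving 20/20/20. With 11 per site the totals are 19/18/18, and with 10 they are 17/16/17.

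**Predictability.** Under a known repeating order, 100% of assignments can be foreseen. For comparison, the share guessed correctly by always naming the arm with most places left:

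- Simple concealed randomisation: 1/3 = 33.3%.
- Permuted blocks of 3, size known: (1/3 + 1/2 + 1)/3 = 61.1%; known for certain, 1/3 = 33.3%.
- Permuted blocks of 6, size known: (0.333 + 0.400 + 0.500 + 0.533 + 0.600 + 1)/6 = 56.1%; known for certain, (0.2 + 1)/6 = 20.0%.

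**Possible effect on the 75% mark.** The protocol gives no adherence figures, so every input here is an assumption. Take 40 tool-arm patients, of whom *k* are weaker users; adherence is *a* in stronger users and *b* in weaker users. Then adherence = [*k·b* + (40 − *k*)·*a*]/40. Unsteered, *k* = 40 × 0.20 = 8 or 40 × 0.30 = 12. If half of these are replaced by stronger users, *k* = 4 or 6.

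| Weaker share | *a* / *b* | Unsteered | Half steered |
|---|---|---|---|
| 20% | 0.80 / 0.50 | (4.0 + 25.6)/40 = 74.0% | (2.0 + 28.8)/40 = 77.0% |
| 20% | 0.85 / 0.40 | (3.2 + 27.2)/40 = 76.0% | (1.6 + 30.6)/40 = 80.5% |
| 30% | 0.80 / 0.50 | (6.0 + 22.4)/40 = 71.0% | (3.0 + 27.2)/40 = 75.5% |
| 30% | 0.85 / 0.40 | (4.8 + 23.8)/40 = 71.5% | (2.4 + 28.9)/40 = 78.25% |

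Three of the four rows move from below 75% to above it; one is above without any steering. The other pairings of the same values, by the same formula, are:

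- 0.80/0.40: 72.0% to 76.0% (20% weaker) and 68.0% to 74.0% (30% weaker).
- 0.85/0.50: 78.0% to 81.5% (20% weaker) and 74.5% to 79.75% (30% weaker).

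The shift is (number moved/40) × (*a* − *b*). Over all eight cases it runs from 4/40 × 0.30 = 3.0 points to 6/40 × 0.45 = 6.75 points.

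If the 75% is read as the proportion of patients who comply, and each patient is given the average chance from the table, the binomial probability of at least 30 of 40 complying is 0.36–0.64 unsteered and 0.61–0.86 with half steered. Section 3.2.1 does not say whether the 75% applies to patients or to scheduled uses, so these probabilities hold for that reading only.

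**The case against.** The case against giving this much weight is substantial, and most of it stands.

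- **Study type.** This is a descriptive feasibility study that does not claim randomisation and plans no between-arm test, so no error rate is affected. That stands. But there is a stated acceptability mark, and descriptive reporting does not remove selection.
- **Holding patients back.** Entry must precede treatment, and planned accrual is one patient per site per month. From a tool slot the standard arm is one or two enrolments away, so roughly one to two months, and many patients would have started treatment by then. That stands, and it narrows the route to selective invitation and order of approach.
- **Degree of steering.** The half-steered cases, if done by swapping, leave the standard arm with 8 weaker users of 20 instead of 4, or 12 instead of 6. That is a lot, and nothing shows that it would happen.
- **Safeguards.** Every arm excludes patients who are "Not capable of using mobile phone applications, or no carer who is willing to and able to use the applications on the participants behalf". Section 5.2 allows carer support with access, and section 5.7.2 provides training. These narrow the range of app ability but do not remove weaker users.

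Three stronger readings are tempting, and the documents do not support them. A reader might infer harm from the numbering ("trial identifier based on study, site and chronological order e.g. PRONL001; PRONL002"), since the number reveals the arm. But the arms are openly different and the arm is recorded, so this adds little. A reader might infer that a difference between video and questionnaire would be selection. Reluctance to use an app explains movement out of both tool arms, but nothing in the protocol gives a reason for steering between them. And a reader might take 1;2;3 to mean consecutive runs of patients, which would confound arm with calendar time; the protocol states no run length.

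**Conclusion.** The weakness is real: the protocol fixes a foreseeable, non-random arm order and leaves selection to treating physicians. It opens tool-arm adherence and withdrawals to bias in the favourable direction. Under the assumed inputs, steering half of the weaker users would raise adherence by about 3 to 7 points, enough to cross 75% in some cases but not all. The actual size is unknown.

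This rests on two inferences. The order is taken to repeat after three patients, which is the natural reading with up to 12 per site but is not stated. Physicians are taken to know the order because it is printed and no concealment is described; the protocol does not say who holds the running list. Steering is a possibility, not a documented event.

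A reader might infer that the results could not be used. The documents do not support that, because no stated inference depends on random allocation. This is a cheap improvement: recommended, not a must-fix.

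**What to change.** Replace the printed rotation with a centrally generated, concealed random list, stratified by site, in permuted blocks of undisclosed mixed sizes (for example 3 and 6). Release each assignment only after consent and eligibility are recorded, and remove the sequence from the protocol.

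This does not make the next arm wholly unpredictable, because sites see past assignments. A single known block size of 3 or 6 would still leave about 61% or 56% guessable, against 100% now. Mixing the sizes and keeping them undisclosed should lower that, though no figure was calculated for the mixed scheme.

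The cost is a short amendment and a small set-up task for the list and its release. There are no extra patients or procedures, and the sample size stays at 60. Arm counts may differ by one or two per site.

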5.7.1 Quality of Life paper questionnaire

This study will use a standard QoL monitoring questionnaire (EQ5D5L). Participants on all arms will complete a QoL questionnaire after consent but before C1D1, during any hospital visit in the 4-week trial period (only when allocated to the QoL arm) and at the end of the study.

5.7.2 PROACT 2.0

If allocated to an arm requiring the use of the app, participants will be provided with training on how to use PROACT 2.0.

PROACT 2.0 is a digital healthcare solution that allows users to record video, voice, text messages and undertake digital questionnaires which can be accessed directly by their care teams. For the purpose of this study, videos will not be reviewed by the patient's care team until after 30 days of receiving the message.

Participants on the PROACT 2.0 arms will be required to use the application every day for the duration of the 4-week study. Patients on the video arm will be asked to record any information on symptoms or impact of treatment – whether positive or negative. Participants on the digital questionnaire arm will answer questions about adverse events experienced in the previous 24 hours. If participants are concerned about their symptoms, they are to follow standard procedure and contact their care team directly and not through the PROACT 2.0 app.

5.8 Trial Visits

When a participant attends a standard trial visit whilst on a phase 1-2 trial, both scheduled and unscheduled, the following information will be recorded for the feasibility study:

- End date of study treatment, if applicable.
- The reason to end participation in the study

5.9 End of study visit

After the 4-week study period, participants will attend for their end of study visit; this will be when they next attend for their drug trial visit. At the end of study visit, participants will be asked to complete a questionnaire to assess their experience of the study. Additionally, they will be required to complete one last QoL monitoring questionnaire.

The following information will also be collected from patients by the healthcare professional.

• WHO performance status

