3.2.2 Secondary outcomes

The secondary outcomes are

- End of study questionnaire complete by patients.
- Semi-structured interviews with healthcare professionals.

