5.10 Qualitative assessments

At the end of the study period, eligible participants will be asked to complete the end of study questionnaire to assess their experiences with PROACT 2.0. Participants will be asked a series of questions relating to their experience of the process and all aspects of the study. The questions will broadly assess the following parameters:

- Overall impressions of the study.
- Opinions on the app functionality they were allocated to, if applicable.
- Adherence to and opinion of scheduling.
- Any further reflections or observations.

On completion of the study, eligible healthcare professionals (those involved in this study) will be requested to participate in a semi-structured interview to assess their experiences with PROACT 2.0. Participants will be asked a series of questions relating to their experience of the process and all aspects of the study. The questions will broadly assess the following parameters:

- Overall impressions of the study.
- Opinions on the app.
- Adherence to and opinion of scheduling.
- Any further reflections or observations.

All interviews should last no longer than 1 hour and will take place virtually. Interviews will be led by a member of the study team, who will transcribe the responses received to each question.

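### The experience questionnaire and final EQ-5D-5L are scheduled only at a drug-trial visit after week 4, with no provision for patients who leave before then

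*Protocol*

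**What the plan says.** The patient half of the secondary outcome in Protocol section 3.2.2 is "End of study questionnaire complete by patients". The other half is "Semi-structured interviews with healthcare professionals".

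Section 5.9 fixes when patients are asked. After the four weeks, "participants will attend for their end of study visit; this will be when they next attend for their drug trial visit". It continues: "At the end of study visit, participants will be asked to complete a questionnaire to assess their experience of the study". The last EQ-5D-5L is completed at the same visit. Section 5.10 gives a similar time and adds a restriction: "At the end of the study period, eligible participants will be asked to complete the end of study questionnaire". It does not say which patients are eligible. Table 1 marks the end-of-study questionnaire only in the column from day 29 on and has no column for early exit.

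For patients who leave early, section 5.8 records the end date of treatment and "The reason to end participation in the study". Section 5.5 asks for the reason for withdrawal where it can be obtained. Section 5.3 limits what may follow. After withdrawal of consent, "No further clinical data will be collected from the study participant". After loss of the ability to consent, "the reason for withdrawal will be documented by the team but no further information will be collected". Section 5.3 states no such limit for the other listed reasons, which include safety and severe non-compliance.

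**The concern.** The schedule makes the questionnaire depend on a drug-trial visit after day 28. A patient who leaves the drug trial in week 2, or is withdrawn from this study, may have no such visit, and no step asks for their experience before they go. What remains is a reason for leaving and, where it applies, a treatment end date.

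This group matters because of what the study sets out to learn. Section 9.1 names patient burden as a risk, says that part of the purpose is to find out whether the daily task adds to it, and puts that discussion at the end of the study. Patients who left because of burden are the ones this timing can miss. If their experience was worse than that of patients who stayed, a favourable proportion taken from those still attending is too high for the enrolled group. An analysis plan cannot repair this, because the answers would not have been collected.

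**Working it through.** **Reproducing the protocol's figures (section 7.1).** Enrolment is 5 sites × 1 patient per month × 12 months = 60. Pre-screens are 60 × (1 + 0.05 + 0.05) = 66, using 5% dropout and 5% screen failure. Both match the protocol and are not in dispute.

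**Who is asked, by route of exit.**

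| Route | Drug-trial visit after day 28? | Asked under the plan? |
|---|---|---|
| Stops using the app, stays in this study and on the drug trial | Yes | Yes |
| Leaves the drug trial before day 29, still consents to this study | Possibly none | No provision if there is no visit |
| Withdrawn from this study (e.g. non-compliance), stays on the drug trial | Yes | Not stated |
| Withdraws consent | Not relevant | No (section 5.3) |
| Loses the ability to consent | Not relevant | No (section 5.3) |

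The second and third rows are the gap that can be closed.

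**Size.** Let *d* be the share of enrolled patients not asked, *p* the favourable proportion among those asked, and *q* the proportion that leavers would have given. The value for all enrolled patients is (1 − *d*)*p* + *dq*, so the overstatement is *p* − [(1 − *d*)*p* + *dq*] = *d*(*p* − *q*).

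Inputs: *d* = 5% is the dropout rate in section 7.1, and *N* = 60 is the sample size there. Everything else is assumed: *p* = 80%, *q* = 20% (or 40% as a milder case), and *d* = 10% or 20%. The protocol gives no rate for leaving the parent drug trial within 28 days.

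| *d* | Not asked | Asked | Overstatement, *q* = 20% | Overstatement, *q* = 40% | Bounds for all 60 |
|---|---|---|---|---|---|
| 5% | 3 | 57 | 0.05 × 0.60 = 3 points | 0.05 × 0.40 = 2 points | 76% to 81% |
| 10% | 6 | 54 | 0.10 × 0.60 = 6 points | 4 points | 72% to 82% |
| 20% | 12 | 48 | 0.20 × 0.60 = 12 points | 8 points | 64% to 84% |

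The bounds need no assumption about *q*. The lower bound counts every leaver as unfavourable and the upper bound counts every leaver as favourable. At 5%: 0.80 × 57 / 60 = 76%, and (0.80 × 57 + 3) / 60 = 81%.

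The table treats every dropout as not asked. Some may still attend and be asked, so for a given *d* the figures are upper values.

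**The case against.** **Poor users are still asked.** A reader might infer that anyone who gives up on the app is lost. The text does not support that. The visit depends on drug-trial attendance, not app use, and the questionnaire covers adherence and views on scheduling. A patient who abandons the app but stays on the drug trial is asked unless withdrawn for severe non-compliance, which is a judgement. This stands, and it narrows the point to patients no longer attending or withdrawn from the study.

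**The exclusion is inferred from silence.** Nothing forbids asking a leaver. Eligible is undefined for patients in section 5.10, the day-29 column has no upper limit, and section 5.3 does not list the end of drug-trial treatment as a reason for withdrawal. Visits may continue after treatment ends. This also stands: the accurate statement is that no provision is made. But a site following sections 5.9 and 5.10 and Table 1 would have no step that prompts it to ask.

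**The negative signal is partly captured elsewhere.** Withdrawals and daily compliance are the primary outcomes, and reasons for leaving are recorded. That is true, but a count and a reason do not replace the experience questionnaire.

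**The size is small and rests on assumptions.** At the protocol's 5%, the overstatement is about 3 points even with a 60-point gap. With 20 patients in an arm (an equal split, assumed), 16 of 20 favourable has a Wilson 95% interval of about 58% to 92%, far wider than that. This stands as to size. A shift of 15 points would need 25% early exit, five times the planned rate, and nothing in the protocol supports that figure.

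**A biased comparison of tools.** A reader might infer this if video were abandoned more often than the digital questionnaire. The protocol gives no evidence on that, states only descriptive analysis and names no between-arm test. The inference is speculative.

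**Conclusion.** The point holds in a limited form. As written, the plan collects patients' experience and the final EQ-5D-5L only from those who attend a drug-trial visit from day 29 on. It makes no provision for patients who leave the drug trial or are withdrawn from this study earlier. The result describes patients still attending after day 28. That is not the same group as patients who complied with daily use.

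At the stated 5% dropout, about 3 of 60 patients are missed, and the overstatement is about 3 points under the assumed 80% against 20%. It would be 6 to 12 points if early exit were 10% to 20%, which is possible but not supported by any figure in the protocol. The direction of the bias is also an assumption: it requires leavers to be less favourable than those who stay.

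The effect is confined to the patient half of a descriptive secondary outcome and to one time point of an exploratory one. The interviews with healthcare professionals are unaffected. It is worth correcting because the remedy is cheap and the missing group bears on the burden question in section 9.1.

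**What to change.** In sections 5.9 and 5.10 and in Table 1, offer the existing end-of-study questionnaire and EQ-5D-5L at day 29 or at exit from this study or the drug trial, whichever comes first. Allow completion by phone or remotely when no visit is due. Offer this to all allocated patients who have not withdrawn consent and who retain capacity, and define eligible in section 5.10 to match. Add an early-exit column to Table 1.

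Report how many patients were asked and how many answered, out of all enrolled. This may sit in the analysis plan, which was not available for this review.

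The cost is a small amendment using existing forms, a few extra contacts, some mixing of completion modes, and variable timing of the final EQ-5D-5L. Recording the date and mode of each completion would let readers judge the last two. Loss from withdrawn consent or lost capacity remains, so the change reduces the selection but does not remove it.
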